Source(s) of Monetary or Material Support	William F. Milton Fund Generative AI Track
Primary Sponsor	Harvard University
Contact for Public Queries	[name] ([contact])
Contact for Scientific Queries	[name] ([contact])
Public Title	Using Conversational AI to Teach Growth Mindset Skills to Youths in India
Scientific title	Using Conversational AI to Teach Growth Mindset Skills to Youths in India: Protocol for a Randomized Controlled Trial
Countries of Recruitment	India
Health Condition(s) or Problem(s) Studied	Youth mental health; anxiety; depression
Intervention(s)	Growth mindset training via 45-minute interaction with conversational AI
Key Inclusion and Exclusion Criteria	
Inclusion Criteria:
 
 - Youth in grades 6-8 at our partner school - Youth assents to participate and a parent/guardian provides passive consent (does not opt-out of participation) 
Exclusion Criteria:
 
 - N/A
Study Type	Interventional
Date of First Enrollment (planned)	Nov 3, 2025
Sample Size	430
Primary outcome(s)	
Change in Behavior and Feelings Survey - Internalizing Subscale (full sample; baseline, 3 weeks, 7 weeks). Trajectories of self-reported symptoms of anxiety and depression from the 6-item (each item rated on a 0-4 scale, with higher ratings indicating more symptoms) Internalizing Subscale of the Behavior and Feelings Survey. Total scores range from 0 to 24, with higher scores indicating more symptoms (BFS; Weisz et al., 2020).
 
Student Perceived Program Acceptability and Helpfulness (intervention group, post-intervention). Assessed via the Program Feedback Scale (Schleider et al., 2019).

Key Secondary outcome(s)	Change in Behavior and Feelings Survey - Internalizing Subscale (elevated subsample ; baseline, 3 weeks, 7 weeks). Trajectories of self-reported symptoms of anxiety and depression from the 6-item (each item rated on a 0-4

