All statistical analyses will be performed using R. To evaluate intervention effects, we will use a series of mixed-effects regression models implemented via the lme4 package (or comparable tools). Each model will include Time (baseline, 3-week, 7-week), Condition (intervention vs. control), and their interaction (Condition \times Time) as fixed effects, with random intercepts for participants and, where feasible, classroom to account for nesting. The Condition \times Time interaction will test whether outcome trajectories differ between groups over time.

If outcome distributions deviate substantially from normality, we may use generalized linear mixed-effects models with an appropriate link function (e.g., logit, log, or beta) or apply suitable transformations (e.g., rescaling data to a (0,1) interval for beta regression) to improve model fit. All models will be checked for assumptions, including residual distribution and heteroskedasticity.

We will calculate both within-subject and between-subject effect sizes for intervention effects on continuous outcomes. For mixed-effects models, standardized mean differences will be computed from estimated marginal means and pooled residual variance (e.g., using effectsize::t_to_d() or contrasts via emmeans). All effect sizes will include 95% confidence intervals and, when available, Common Language (CL) effect sizes to facilitate interpretation.

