For the mediation analysis, we will use structural equation modeling (SEM) in R (lavaan) to test whether change in Growth Mindset mediates the effect of the intervention on change in BFS-Internalizing. The primary model will specify: Intervention \rightarrow Growth Mindset \rightarrow BFS-Internalizing, with baseline levels of both constructs included as covariates. We will use a latent change score (LCS) mediation model or an observed (composite-score) change model. Indirect effects ($a \times b$) will be estimated using bias-corrected bootstrap 95% confidence intervals, and standardized effects will be reported. Missing data will be addressed using Full Information Maximum Likelihood (FIML) or pooled multiple imputation, consistent with the main analysis. Because indirect effects are typically smaller than direct effects, and given the available sample size ($N \approx 430$), we expect adequate power to detect small-to-moderate indirect effects but limited power for very small ones. Accordingly, this mediation analysis is secondary and exploratory, and findings will be interpreted cautiously.

Transformations

We will examine the distribution of each outcome and apply transformations or generalized linear mixed-effects models as appropriate. For example, if data are heavily right-skewed, we may rescale continuous outcomes to a (0,1) range and fit a **beta-distributed model** to better approximate the observed distribution.

Inference criteria

Two-tailed tests ($\alpha = .05$) will be used.

27b. Definition of who will be included in each analysis and in which group

Participants enter the analysis cohort at randomization, which occurs after assent and baseline measures. Assenting students will be excluded if they do not have the opportunity to complete the baseline measures (e.g., due to interruption or absence) or if they later withdraw consent or assent and ask for their data to be excluded; all others will be included.

All planned analyses will be conducted using the full participant sample (intention-to-treat). We will also conduct subgroup analyses among students with elevated baseline internalizing symptoms—defined as scores ≥ 1 SD above the mean—following established norms for youth mental health measures (e.g., Youth Self-Report; Achenbach & Rescorla, 2001). These analyses will explore whether intervention effects differ when the program is used as a universal versus indicated prevention approach.

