27c. How missing data will be handled in the analysis

We will address missing data using **multiple imputation** via the **mice** package in R. Prior to imputation, we will examine patterns of missingness and conduct sensitivity analyses to assess whether data appear to be **missing at random (MAR)** versus systematically missing. Imputation models will include all variables used in the main analyses and relevant auxiliary variables to support the MAR assumption.

Appropriate imputation methods will be specified by variable type (e.g., predictive mean matching for continuous variables, logistic or polytomous regression for categorical data). For bounded or highly skewed variables, we may apply transformations (e.g., logit or log) prior to imputation and back-transform results after pooling. If multilevel dependencies (e.g., students nested within classrooms) substantially affect missingness patterns, we will use multilevel imputation approaches (e.g., miceadds or mitml) to preserve the nested data structure.

The number of imputed datasets will approximately match the percentage of missing data for each outcome (rounded up to the nearest whole number, e.g., three imputations for $\sim 2\text{--}3\%$ missingness). Analyses will be pooled across imputations using **Rubin's rules**, providing **intent-to-treat** estimates that retain power and reduce bias relative to listwise deletion.

Effect sizes (e.g., Cohen's d with 95% confidence intervals) will be derived from model-based estimates using the **effectsize** or **MOTE** packages in R, based on t -values from treatment effects in the pooled analyses.

27d. Methods for any additional analyses (e.g., subgroup and sensitivity analyses)

1) We will conduct exploratory qualitative analyses of participants' growth mindset reflections using AI-based text analysis tools, supplemented by manual review where appropriate. In addition to categorizing responses into themes, we will code whether reflections demonstrate (a) valid understandings of growth mindset, (b) positive applications of growth mindset in real-life contexts, or (c) specific intentions to apply growth mindset principles. We will also explore whether baseline demographic variables are associated with the presence or absence of these codes.

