- 2) We will conduct exploratory qualitative analyses of chatbot interaction logs using AI-based text analysis tools, supplemented by manual review where appropriate. Analyses may include descriptive summaries of responses (e.g., response length, number of attempts required to generate acceptable answers) and thematic analyses of key responses (e.g., categorization of advice provided in role-playing scenarios).
- 3) We may explore the time taken by participants to progress through each step of the chatbot, including optional examination of how baseline demographic variables are associated with those timings.
- 4) If many participants are unable to finish the training in the allotted time, we may perform an additional analysis with the subsample of participants who were able to finish the complete training.
- 5) We may explore how various baseline variables moderate the effectiveness of the intervention. For example, we may examine whether baseline demographic variables or baseline measures of internalizing symptoms moderate changes in outcome variables over time.

Methods: Monitoring

28. Data monitoring committee

28a. Composition of data monitoring committee (DMC) or an explanation of why it is not needed
There will not be a formal Data Monitoring Committee for this trial, as the study involves minimal risk to participants. Ongoing oversight will be conducted by the research team, who will monitor data quality, participant safety, and ethical compliance throughout the study.

28b. Explanation of any interim analyses and stopping guidelines

N/A

29. Trial monitoring

No formal trial monitoring is planned for this study, as it involves minimal risk to participants and is conducted at a single school site under direct supervision of the research team.

Ethics

30. Research ethics approval

This study was approved by the Harvard University-Area Committee on the Use of Human Subjects.

The original submission (ID number: IRB25-0827) was approved on 9/19/2025.

A modification was submitted to spread the intervention across two class periods, and to provide a booklet with the full intervention material at the conclusion of the study. The modification (ID number: MOD25-0827-01) was approved on 10/10/2025.

31. Protocol amendments

Any substantive protocol changes will be approved by the Harvard IRB and updated in this document and the trial registry.

32. Consent or assent

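### Within-arm effect sizes in the elevated subsample would include regression to the mean, and no committed model term tests whether effects differ by baseline severity

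*Combined protocol and SAP*

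**What the plan says.** - Section 27a, on effect sizes: "We will calculate both within-subject and between-subject effect sizes for intervention effects on continuous outcomes". For the mixed models, "standardized mean differences will be computed from estimated marginal means and pooled residual variance".
- Section 27a, on the models: "Each model will include Time (baseline, 3-week, 7-week), Condition (intervention vs. control), and their interaction". No term for baseline severity or subgroup membership is listed. The Condition × Time interaction carries the inference.
- Section 1b lists among the key secondary outcomes the BFS "Internalizing Subscale (elevated subsample ; baseline, 3 weeks, 7 weeks"). Section 16 repeats it.
- Section 27b plans "subgroup analyses among students with elevated baseline internalizing symptoms", with a cut-off one SD above the mean, and gives the purpose: "These analyses will explore whether intervention effects differ when the program is used as a universal versus indicated prevention approach".
- Section 27c derives effect sizes from t-values "from treatment effects in the pooled analyses". It does not withdraw the within-subject effect sizes of Section 27a.
- Section 27d, item 5, mentions, only as a possibility, examining whether "baseline measures of internalizing symptoms moderate changes in outcome variables over time".

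**The concern.** There are two linked problems.

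First, students enter the elevated subsample because their observed baseline score is high. Part of that height is transient, so their later scores are expected to be lower whatever they receive. A pre-post effect size in the intervention arm of this subsample therefore mixes any benefit with regression to the mean. Section 27a nevertheless describes within-subject effect sizes as measures of intervention effects. An ineffective chatbot could appear to have a large effect in the students of most clinical interest.

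Second, a model fitted only in the elevated students estimates the effect in those students. It does not estimate how that effect differs from the effect in anyone else. Setting it beside the full-sample result is not a test either, because the full sample contains the subgroup. The committed output is two results of very different precision, and a reader could easily take a gap in significance for a gap in benefit.

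**Working it through.** **Inputs from the documents.** About 430 students, from 450 × 0.95 = 427.5; 1:1 simple randomisation; cut-off at +1 SD; two-sided α = 0.05; power 80%; detectable effect 0.22 (Sections 19, 21b, 27a and 27b).

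**Assumptions.** The correlation r between visits is not given, so 0.5, 0.67 and 0.8 are used, equal across the three visits. Scores are taken as normal, the cut-off as sample-based, data as complete and classroom effects as absent.

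**The plan's own figure.** Comparing one follow-up without using baseline, the detectable effect is (1.960 + 0.842) × √(4/430) = 0.270 SD. The stated 0.22 needs an unstated r: about 0.58 for ANCOVA at one follow-up (factor √(1 − r²)), or about 0.67 for a change score (factor √(2(1 − r))). So 0.22 is plausible but cannot be confirmed. Its metric is not defined; below it is read as full-sample SD.

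**Part 1: zero treatment effect.**

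1. P(z ≥ 1) = 0.159, so the subgroup has 430 × 0.159 ≈ 68 students, about 34 per arm.
2. E[z | z ≥ 1] = 1.525, and the variance of z in that tail is 0.199.
3. Expected drop in each arm = (1 − r) × 1.525.
4. SD of change = √((1 − r)² × 0.199 + 1 − r²).
5. Within-arm t = drop ÷ (SD of change ÷ √34).
6. The residual SD of the planned random-intercept model, fitted in the subsample, was obtained by simulation.

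| | r = 0.5 | r = 0.67 | r = 0.8 |
|---|---|---|---|
| Drop (full-sample SD) | 0.763 | 0.503 | 0.305 |
| SD of change | 0.894 | 0.757 | 0.607 |
| Within-arm t | 4.97 | 3.88 | 2.93 |
| Residual SD | 0.659 | 0.549 | 0.435 |
| Drop ÷ residual SD | 1.16 | 0.92 | 0.70 |
| Simulated within-arm effect size, intervention vs control | 1.16 vs 1.17 | 0.92 vs 0.92 | 0.71 vs 0.71 |
| Between-arm rejection in subgroup | 5.0% | 5.0% | 4.8% |

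The last two rows come from 6,000 simulated trials of 430 per value of r, using the 2-df Condition × Time test. The raw drop is 0.305/0.22 = 1.4 to 0.763/0.22 = 3.5 times the effect the trial is sized to detect.

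In a separate simulation of 4,000 null trials per setting, the within-arm test of change to the last visit excluded zero in 99.8% of trials at r = 0.5 and 81% at r = 0.8. With an assumed right-skewed 0–24 score, about 57 students were selected. The drop was then larger, about 1.2 to 0.54 SD, and zero was excluded in 98% to 66% of null trials.

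**Part 2: the same benefit of 0.22 SD for every student, at both follow-ups.**

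| | r = 0.5 | r = 0.67 | r = 0.8 |
|---|---|---|---|
| Full sample significant | 65% | 84% | 97% |
| Subgroup significant | 16% | 20% | 29% |
| Full sample significant, subgroup not | 52% | 65% | 68% |
| Condition × baseline BFS test significant | 4.9% | 4.4% | 4.7% |

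The interaction test regressed the mean of the two follow-ups on condition, baseline and their product in the full sample. There is no true difference here, so its rejection rate of about 5% is the correct one.

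**Power of a direct comparison.** For 68 elevated against 362 other students at one follow-up, the detectable difference at 80% power is 2.802 × √(4/68 + 4/362) = 0.74 SD. Scaled to the plan's own 0.22, it is 0.74 × 0.22/0.270 ≈ 0.60 SD.

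**The case against.** The strongest reply is that the trial's inference is sound. Condition × Time is a randomised contrast and selection uses a pre-randomisation score, so regression to the mean is expected equally in both arms and cancels. The simulated 5% rejection rate confirms this. The plan also promises between-subject effect sizes with confidence intervals, so an honest figure would stand beside the within-subject one. All of this stands, and it limits the point to the within-arm figures.

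A second reply is that within-subject may mean the Condition × Time contrast standardised on a within-person scale, which the t-value wording in Section 27c could support. Regression to the mean would then cancel there too. The text does not say so, and one sentence would settle it.

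A third is that Section 27d, item 5, already names baseline symptoms as a possible moderator, and that the subgroup work is exploratory. The item is optional, however, and is not linked to the universal-versus-indicated question. An exploratory question still needs a quantity that answers it.

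A fourth is that nothing in the plan says a gap in significance will be read as a gap in effect, and that the 52% to 68% mainly reflects low subgroup power. That is fair. The percentages show how misleading the only committed outputs could be, not a rule the authors have adopted.

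Finally, the magnitudes depend on assumptions. The residual-scaled figure also depends on the standardiser: with the full-sample residual SD, √(1 − r), it is 0.763/0.707 = 1.08 at r = 0.5 and 0.305/0.447 = 0.68 at r = 0.8. The direction and rough size do not change.

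**Conclusion.** The concern holds in both parts. As Section 27a is worded, the elevated subsample would receive a within-subject effect size presented as an intervention effect. Its expected value with no benefit at all is about 0.7 to 1.2 residual SD, for assumed correlations of 0.8 down to 0.5 and normal scores. Between-arm estimates and tests are not biased by this.

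The question in Section 27b, whether effects differ between universal and indicated use, has no committed estimate. The two results that are committed would disagree on significance in more than half of trials under an identical 0.22 SD benefit, given the same assumptions. The correlation, the score distribution and the metric of 0.22 are not in the documents, so these figures are ranges, not predictions.

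**What to change.** 1. In Section 27a, state that only between-arm contrasts estimate intervention effects. Present within-arm change as descriptive and always for both arms side by side, with a note on regression to the mean for the elevated subsample. If within-subject was meant as a standardisation of Condition × Time, say so.
2. For the universal-versus-indicated question, commit to one full-sample model of the 3- and 7-week BFS. Enter baseline BFS as a continuous covariate, so that it is not also an outcome, and include a Condition × baseline BFS interaction. Report the interaction with its confidence interval, and the between-arm effect at the mean and at +1 SD of baseline.
3. Keep the subgroup-only estimate as descriptive. State whether the cut-off uses the sample mean and SD or external norms, since Section 27b refers to both, and report the resulting number of students.
4. State in advance that the interaction has limited power, so a non-significant result does not show equal benefit.

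The cost is SAP wording and one further model on data already being collected. The subgroup results will look less striking. The interaction assumes that the effect changes linearly with baseline BFS, which needs a check.

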Change in Growth Mindset Beliefs (all participants; baseline, 3 weeks, 7 weeks) - Assessed via the Growth Mindset Scale (Sigmundsson & Haga, 2024), adapted to a 6th grade reading level. This scale consists of 8 items, rated on a scale from 1 (not like me at all) to 5 (very much like me).

- In one sentence, what is the main idea of growth mindset?
- Have you used growth mindset for anything at school or home in the past few weeks?
 - o Yes
 - o Not yet
 - o I'm not sure
- [If they answer "Yes"] Please share what happened. What did you do or think?
- How might you use growth mindset in the next month? Be sure to explain:
 - o WHAT you want to get better at. This could be a school subject, a skill, or any personal goal.

- HOW you will improve. This could include practicing, asking for help, or any of the tips above!

Chatbot logs: The logs of all interactions with the chatbot, including timing of messages, will be recorded for analysis.

Potential Moderators:

Demographic questions: age, gender identification, sex assigned at birth, year in school.

Potential Mediator:

Growth Mindset Beliefs: We will conduct a secondary mediation analysis using structural equation modeling (SEM) to test whether change in Growth Mindset mediates the effect of the intervention on change in BFS-Internalizing.

17. Harms

Participants may feel uncomfortable answering some measures of their mental health.

Participants will be told that they have the option to not respond to the questions if they feel uncomfortable or they can rescind their participation in the study. Furthermore, to protect participant responses, we will use a codebook of coded IDs (maintained and owned by the school) so that all IDs collected for research are coded. Given these precautions, we do not anticipate any significant risks associated with this study.

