		X			X	X
				X		
					X	X
Growth mindset reflections (intervention group)						

19. Sample size

Our sample size is constrained by the number of available students in the school. We expect about 450 students to be invited to participate (150/students per grade across 3 grades). Assuming an opt-out rate of 5%, we can expect a sample size of about 430 students.

For our primary tests of intervention effects (i.e., mixed effects model examining the time [baseline, 3-week FU, 7-week FU] * condition [Intervention or Control] interaction), an a priori power analysis shows that our sample size can detect effects as small as 0.22 (using two-tailed tests with $\alpha = .05$, $\beta = 0.2$). This effect size is comparable to that detected by a prior single-session growth mindset intervention (Schleider & Weisz, 2018).

20. Recruitment

All students in grades 6-8 at our partner school will be invited to participate.

The school partner was based on strong pre-existing relationships with the research team. The decision to focus on grades 6-8 was made in consultation with the school principal, who believed that these grades would benefit from the intervention while also having flexibility in their curriculum.

Methods: Assignment of interventions

21. Randomization: Sequence generation

21a. Who will generate the random allocation sequence and the method used

The first author will perform the randomization using R.

21b. Type of randomization (simple or restricted) and details of any factors for stratification.

Simple individual randomization (1:1) of participants to intervention or control group.

22. Allocation concealment mechanism

The use of central randomization will ensure that students and teachers cannot determine trial allocation ahead of time. Allocation to the experimental or control groups will take place when class is not in session (between the day of enrollment and the start of the intervention.)

23. Implementation of randomization

As the study procedures are conducted online, assignment of participants to intervention or control groups is done electronically and not by any personnel. Hence no personnel can influence the implementation of the randomized assignment.

24. Blinding

24a. Who will be blinded after assignment to interventions (e.g., participants, care providers, outcome assessors, data analysts)

The intervention will be unblinded for teachers, students and researchers.

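### The plan's two effect-size rules, residual SD and t-to-d, give different values of d for the Condition × Time contrast, and neither is assigned to the promised within- or between-subject d

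*Combined protocol and SAP*

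**What the plan says.** Section 27a (Statistical models) fits mixed models with Time, Condition and their interaction, random intercepts for participants and, where feasible, for classrooms. The interaction is the test of the intervention. On effect sizes the same section makes three statements:

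- "We will calculate both within-subject and between-subject effect sizes for intervention effects on continuous outcomes".
- For mixed models, "standardized mean differences will be computed from estimated marginal means and pooled residual variance".
- As examples of how to do so, "using effectsize::t_to_d() or contrasts via emmeans".

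Section 27c (missing data) derives Cohen's d and its 95% CI after multiple imputation with the effectsize or MOTE packages, based on t-"values from treatment effects in the pooled analyses". It states neither the df nor the n that enters the conversion.

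The rules apply to BFS-Internalizing and to the Growth Mindset Scale (Section 16: "Change in Growth Mindset Beliefs (all participants; baseline, 3 weeks, 7 weeks"). Two further provisions matter for the remedy. Under Transformations, "we may rescale continuous outcomes to a (0,1) range and fit a" beta model. In Section 27b, "We will also conduct subgroup analyses among students with elevated baseline internalizing symptoms". Section 19 states that "our sample size can detect effects as small as 0.22" and compares this with the effect in a prior single-session trial, without naming the contrast or the standardizer.

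**The concern.** Dividing a difference by the residual SD and converting a t-value to d answer different questions once the model holds a participant intercept and the contrast is a difference in change. The residual SD leaves out stable differences between students. The t-value reflects the standard error of a change contrast, so a conversion built for two independent groups does not return the difference over an ordinary between-student SD. Section 27a offers the second as a way of computing the first, and Section 27c then relies on t-values alone.

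Two analysts who follow the plan could therefore report clearly different values of d, each with its own CI, from one fitted model of a primary outcome. A reader could take a residual-SD value for a between-student effect, and could not tell which reported d belongs beside the 0.22 in Section 19. The within- and between-subject effect sizes are promised, but no formula is tied to either.

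**Working it through.** **Inputs from the documents.** About 430 students, 1:1 allocation, so about 215 per arm (Sections 19 and 21b). Three time points and a participant intercept (27a). Two-sided α 0.05, β 0.2 and a detectable effect of 0.22 (19).

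**Assumptions not in the documents.** Complete data; no classroom variance in the contrast; equal correlation r between waves; total SD of 1 at each wave; pooled residual variance read as the level-1 residual variance, so σₑ² = 1 − r; conversion d = 2t/√df. Two candidate df: 430 − 2 = 428 and, for within-student contrasts, 428 × 2 = 856. The plan chooses neither.

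**The plan's own figure.** A plain two-sample comparison gives (1.960 + 0.842) × √(2/215) = 0.270, not 0.22. For change at one follow-up, the detectable effect in baseline SDs is 2.802 × √(4(1 − r)/215), which is 0.22 at r of about 0.67. No r is stated, so 0.22 can be neither confirmed nor refuted. For the same one-follow-up contrast the detectable effect is:

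- residual-SD scale: 2.802 × √(4/215) = 0.382;
- t-to-d at df 428: 2 × 2.802/√428 = 0.271;
- t-to-d at df 856: 2 × 2.802/√856 = 0.192.

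So 0.22 has no meaning until its scale is named.

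**Ratio of the two routes.** Let D be the difference in change at one follow-up.

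- SE(D) = σₑ√(4/215).
- Residual-SD route: D/σₑ.
- t route: 2t/√df = 2D/(σₑ√(4/215)√df) = (D/σₑ) × √(215/df).
- Ratio of residual-SD d to t-based d = √(df/215): 1.411 at df 428 and 1.995 at df 856. σₑ cancels, so r plays no part.

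Random-intercept models fitted to simulated three-wave data at r = 0.5, 0.6 and 0.7 gave 1.4109 and 1.9953 in every fit.

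For the mean of both follow-ups minus baseline, SE(D) = σₑ√(3/215) and the ratio is √(1.5 × df/430): 1.22 at df 428 and 1.73 at df 856.

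**Distance from a between-student d.** The residual-SD d is D/√(1 − r), larger than the total-SD d by 1/√(1 − r). The one-follow-up t route gives D × √(215/((1 − r) × df)), which equals D only when (1 − r) × df = 215. That is r = 0.498 at df 428 and r = 0.749 at df 856.

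**Illustration**, true D assumed to be 0.22 baseline SD at one follow-up:

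| r | SE | t | residual-SD d | t-to-d, df 428 | t-to-d, df 856 |
|---|---|---|---|---|---|
| 0.5 | 0.0964 | 2.28 | 0.311 | 0.221 | 0.156 |
| 0.6 | 0.0863 | 2.55 | 0.348 | 0.247 | 0.174 |
| 0.7 | 0.0747 | 2.94 | 0.402 | 0.285 | 0.201 |

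At r = 0.6 the 95% CI in baseline SDs is 0.22 ± 1.96 × 0.0863 = 0.05 to 0.39. Rescaled, it is 0.08 to 0.62 (residual SD), 0.06 to 0.44 (t-to-d, df 428) or 0.04 to 0.31 (t-to-d, df 856).

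**Where t-to-d works.** For a simple between-arm contrast at one follow-up, t = 0.22/√(2/215) = 2.28 and 2t/√428 = 0.221. The conversion is sound there, but that is not the contrast the plan tests.

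**The case against.** The strongest reply is that nothing inferential changes: test, type I error and raw difference are the same whichever d is printed. That stands, and it limits the weight of the point.

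Second, the functions in 27a are only examples, and 27c is more specific, so the t-based rule may be meant to govern the imputed results. That is a fair reading. It still leaves the df open, and it leaves the plan with a d that matches a between-student effect only at particular values of r.

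Third, 27a does not say what the residual variance is pooled over. If it means participant plus residual variance, the inflation by 1/√(1 − r) disappears. This also stands, and the ratios above are conditional on the level-1 reading. The wording does not settle it, which is itself a reason to name the standardizer.

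Fourth, within-subject may simply mean pre-post change inside an arm. That is plausible. A Condition × Time contrast compares arms whatever SD divides it, so a residual-SD version of it should not be called within-subject.

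A reader might take 1.4 to 2 as the range of disagreement. It is not a bound: the mean of both follow-ups gives 1.22 and 1.73, and Rubin-pooled df can move the ratio further. A reader might also infer that the plan would inflate d in the elevated subsample through its narrow baseline SD. Neither stated rule divides by that SD; the matter arises only when a baseline SD is adopted.

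**Conclusion.** The point holds and should be fixed. The plan treats two non-equivalent calculations as interchangeable for its main contrast and ties neither to the effect sizes it promises. For change at one follow-up the residual-SD d is √(df/215) times the t-based d: 1.41 at df 428, 2.00 at df 856. This rests on complete data, 215 per arm, the 2t/√df conversion and the level-1 reading of residual variance. The existence of the mismatch is firm; its size in the final report depends on choices the plan leaves open.

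The damage is confined to the reported d and its CI. The documents do not support the inference that the primary test is invalid, nor that the 0.22 in Section 19 is wrong. Its contrast and scale are unstated, so it cannot be matched to any reported d.

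**What to change.** Amend the effect-size text in 27a and 27c as follows.

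1. For BFS-Internalizing and the Growth Mindset Scale, report the pooled model-estimated between-arm difference in change from baseline at 3 and at 7 weeks, in raw points with 95% CI.
2. Obtain the between-group d by dividing the estimate and its limits by that outcome's pooled full-sample baseline SD. Use the same SD for the elevated subsample. That group is selected on baseline BFS score, and under normality its own BFS SD would be only about 0.45 of the full-sample value.
3. Drop the t-based conversion in both sections for these contrasts.
4. Define the within-subject effect size separately, as within-arm change from baseline, with its standardizer named. Label any residual-SD index as residual-SD-standardized, not as within-subject.
5. If a transformed or link-function model is used, give the raw-scale difference as a descriptive companion to the model-scale test, since the two are then not the same contrast.
6. State in Section 19 the contrast and standardizer behind 0.22.

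The cost is wording and a little code, with no change to design or data. The reported d may be smaller than the residual-SD version. Dividing the limits by a fixed SD ignores that SD's own sampling error, about 1/√(2 × 428) = 3.4%. A link-function model needs an extra step to reach the raw scale.
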